1.2.3 Compare caregiver quality of life

2.0 BACKGROUND, RATIONALE

Hematopoietic stem cell transplantation (HCT) is a complex medical treatment that causes significant symptom burden for patients and their caregivers. Patients receive chemotherapy and/or radiation therapy prior to transplant to eradicate the underlying disease and provide immunosuppression. While the myelosuppressive or myeloablative conditioning regimens used prior to transplant provide medical support to treat underlying disease and provide immunosuppression, they can cause the development of physical,¹ psychological,² and nutritional challenges³⁻⁵ that can impact a patient’s short- and long-term wellness. Allogeneic HCT is associated with treatment related mortality (TRM) ranging from 20-30%.⁶ TRM is particularly high in patients with advanced age, decreased functional status, and/or comorbid conditions such as depression or organ dysfunction. While evaluation of organ dysfunction is required part of pre-transplant workup (echocardiogram, pulmonary function testing, etc.), decreased physical function, cognitive deficits, depression, poor nutrition, and lack of

A Research Program Targeting Pre-, Peri-, and Post-transplant Optimization Program (R-POP)

Version 1.18: October 25, 2022

social support are less often evaluated. This investigation will assess these five domains and implement interventions to improve them.

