Significant challenges of behavioral interventions include monitoring and adherence. By using activity trackers, we will be able to monitor whether patients are meeting their heart rate goal; because data will be available in real-time, research staff can follow up to provide positive feedback to patients who are meeting goals or coaching and assistance to those who are not as successful. Similarly, daily monitoring of dietary intake on the custom HCT app will be supported by wireless transmission and review of the data by a research dietitian, who will give feedback and education to patients on food choices. Our mHealth platform combines existing technology (e.g. Apple Watch, Microsoft Band 2) with custom solutions (HCT app), both of which have already been piloted in Duke HCT patients (IRB Pro00068979, PI [name], co-I [name]) and which patients view favorably as both easy to use and helpful (abstract accepted for presentation at the American Society of Hematology 2017 Annual Meeting).

The following table outlines the assessments each consenting patients will be asked to complete and the interventions directed at each domain; further details are provided in subsections:

Domain	Assessment	Time (min)	Timepoints	Intervention
Physical Activity and Function	Short physical performance battery	0*	6T	Interval training
	6 minute walk	0*	6T	
	30 second sit/stand	0*	6T	
	Grip strength	0*	6T	
	Fried	0*	6T	
	PROMIS Physical Function	2	6T	
	CPET	60	NPE, SO, D30****, DC, D180	
	BodPod or BIA	5	NPE, SO, DC, D180,	
Musclesound	20	Y1 6T (D30****)		

Cognitive Function	Montreal Cognitive Assessment PROMIS Cognitive Function RBANS Trail Making Test Brief Cope	0* 2 30 5 5	6T 6T 6T 6T 6T	Interval training
Mental Health	PHQ9 PC-PTSD/PCL-5 PROMIS Depression PROMIS-Anxiety	0* 0* 2 2	6T 6T 6T 6T	
Nutrition and Diet	Peri-operative nutrition screen PG-SGA Vit D, Vit A, albumin, prealbumin, lipids, A1c; if PONS+ also thiamine, Zn, Cu, selenium** 24 food recall Food Security DHQ3	0* 2 0* 10 2 30	6T 6T 6T 6T NPE, D180, Y1 6T	Daily tracking of food groups
Social Support	PROMIS-Emotional Support PROMIS-Social Isolation Lorig Self Efficacy Two Factor Consideration of Future Consequences Scale (CFC-14) Brief Resilience Scale (BRS)	2 2 2 5 2	6T 6T 6T 6T 6T	
Symptoms	NCCN Distress Thermometer	0*	6T	Per clinical care
Comorbidities	HCT-CI (completed by MD)	0	NPE	Per clinical care
Global	FACT-BMT EQ-5D-5L OARS IADL	0* 0* 0*	6T 6T 6T	NA

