Microbiota	Skin Swab Stool Collection	5 5	6T 6T + D0, 7, 14, 21, Y2	NA
Biomarkers	Blood collection	1	6T + D14	NA
Financial	Financial Assessment	0*	NPE, D90, D180	NA
Activity Data	Heart rate Step count Activity Intensity Sleep	0*** 0*** 0*** 0***	Continuous	Per discussion as part of interval training
Applications	TRU-BMT or SplendoFit	5	Daily thru Year 1	
Polypharmacy and	Case Report Form	0*	SO, D30, D90, D180,	NA

A Research Program Targeting Pre-, Peri-, and Post-transplant Optimization Program (R-POP)

Version 1.18: October 25, 2022

Medication Reconciliation			Y1	
	Total time (patients):	179		

PROMIS=Patient Reported Outcomes Measurement Information System; 6T=6 main timepoints (pre-transplant: new patient evaluation [NPE] and sign off [SO] prior to transplant; peri-transplant: day 30 [D30], discharge home [DC] (approximately D90); post-transplant: day 180 [D180], year 1 [Y1]); CPET=Cardiopulmonary Exercise Test; PC-PTSD-5=Primary Care PTSD for DSM-5; PG-SGA=scored Patient Generated Subjective Global Assessment; A1c=Hemoglobin A1c; PONS=Perioperative Nutrition Score; PONS+=positive PONS; Zn=zinc; Cu=cooper; FACT-GP=Functional Assessment of Cancer Therapy – General Population; PHQ=Patient Health Questionnaire; RBANS= Repeatable Battery for the Assessment of Neuropsychological Status; N/A=not applicable

*Completed as part of standard clinical practice, or with cPOP (Pro00111631) or with blood draws being done as part of standard clinical practice; while this data will be analyzed as part of this study, no additional or minimal additional patient time or involvement is required to collect it.

** Per investigator/MD discretion

*** Data will be collected passively from the Apple Watch and no patient involvement is required to collect data.

**** Will only be collected if subject is medically stable.

While the total anticipated time for assessments is 179 minutes, 85 minutes is cardiopulmonary exercise testing, 11 minutes are related to sample collection, and 83 minutes are questionnaire-based; these will be split into two sessions to minimize patient burden.

Use of previously collected data: If a subject is simultaneously on another study and the same assessment or sample is required for both studies, we will only collect once and share the data between studies to avoid subjects having to duplicate efforts.

Collection Windows:

New Patient Evaluation: +30 days of New Patient Evaluation Clinical appointment

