4.4 Nutrition and diet

4.4.1 Patient Generated Subjective Global Assessment

The scored Patient-Generated Subjective Global Assessment (PG-SGA) is a quick and accurate nutrition assessment tool that has been used in the oncology¹⁰⁵ and HCT³⁵ settings. As a revision of the Subjective Global Assessment,¹⁰⁶ it evaluates an individual’s physical status as it relates to nutrition and nutritional impact symptoms. The patient completes sections 1 through 4 (i.e. Weight, Food Intake, Symptoms, and Activities and Function), while the health professional evaluates Worksheet 2 - Disease and its relation to nutritional requirements (Section 5), Worksheet 3 - Metabolic Demand (Section 6), and performs Worksheet 4 - Physical Exam (Section 7). Additionally, the health professional completes Worksheet 1 to score weight loss (if applicable) and Worksheet 5 to provide a subjective global rating of the respondent’s overall nutritional status (e.g. well-nourished, moderately malnourished, or severely malnourished). Scores for each section can range from 0-4 depending on severity and nutritional impact. The sum of all scores provides the Total PG-SGA score, which can be used to indicate the need for intervention.¹⁰⁵ For example, a score of ≥ 9 indicates a need for critical intervention.

4.4.2 24- Hour food recalls RPOP participants will be called at the 6T by a study team member to review their dietary intake for the previous 24 hours. The participants will just be responsible for reporting food intake to the study team member and they will record in their study records.

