6.0 STATISTICAL CONSIDERATIONS

General Considerations: All analyses will be summarized using appropriate effect estimates, confidence intervals, and p-values. All secondary and additional analyses will be evaluated at the standard 0.05 significance level. Descriptive statistics, including graphical displays, will be used to summarize all study variables. For continuous variables, means, standard deviations, percentiles, ranges, box plots and histograms will be generated. For categorical variables, frequencies and proportions will be generated. For time to event variables, event rates and survival curves will be generated. Statistical analyses will be performed using SAS for Windows (Version 9.3 or above: SAS Institute, Cary, NC) and the R statistical computing platform (R Core Team 2013; <http://www.R-project.org/>).

Categorical outcomes will be analyzed using chi-square techniques and logistic regression modeling. Length of stay outcomes will be analyzed using generalized linear models with appropriate link functions. Continuous, longitudinal outcomes such as the FACT-BMT and EQ-5D-5L will be analyzed using linear mixed regression modeling. Other continuous results (such as PG-SGA and numbers of days exercised and amount of exercise per day) will be analyzed using standard t-test approaches and correlated with outcomes. We will analyze TRM and CTCAE using Kaplan-Meier methods, log-rank tests, and Cox proportional hazard regression modeling.

6.1 Analysis of the Microbiota:

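### PG-SGA is measured at six visits but is assigned to an unspecified t-test instead of the plan's mixed model, which discards visits and may bias the change in either direction

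*Combined protocol and SAP*

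**What the plan says.** Section 6.0 (Statistical Considerations) separates continuous outcomes into two groups. For the first: "Continuous, longitudinal outcomes such as the FACT-BMT and EQ-5D-5L will be analyzed using linear mixed regression modeling". The next sentence covers the rest: "Other continuous results (such as PG-SGA and numbers of days exercised and amount of exercise per day) will be analyzed using standard t-test approaches". It adds that these results will be correlated with outcomes.

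The assessment table in section 4.0 lists the nutrition items in the order "Peri-operative nutrition screen PG-SGA Vit D, Vit A, albumin, prealbumin, lipids, A1c" and so on, with timepoints "6T 6T 6T 6T NPE, D180, Y1 6T". PG-SGA is the second item, so it is a 6T measure. The table's footnote defines 6T as new patient evaluation (NPE), sign off (SO), day 30, discharge at about day 90 (DC), day 180 and year 1 (Y1). The Global row, "FACT-BMT EQ-5D-5L OARS IADL", carries 6T for every item.

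On direction, section 4.4.1 says: "For example, a score of ≥ 9 indicates a need for critical intervention". Higher is therefore worse. On expected loss, section 2.0 says "Allogeneic HCT is associated with treatment related mortality (TRM) ranging from 20-30" per cent and adds that it is higher with poor function or comorbidity. Section 7.0 gives 10-30%. Section 6 has no rule for missing data or death.

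**The concern.** PG-SGA has the same repeated-measures structure as the two scores given a mixed model, yet it is grouped with exercise counts. A t-test compares two means, so at most two of the six visits enter any one comparison. In a single-arm study (section 3.5) there is no control group, so the natural use is change from NPE to a later visit. Patients without the later score either drop out (paired) or contribute only to the NPE mean (unpaired). If they differ from those who remain, the estimated change is distorted.

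Diet and nutrition is one of the domains named in the primary objective (section 1.1), and section 7.0 says the study should inform a randomized phase 2 trial. A distorted PG-SGA change could carry into that design.

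**Working it through.** **The plan's only attrition figure.** Section 6.2 allows 10% for failing the exercise test and consents 35 so that 30 are treated. 30/(1 - 0.10) = 33.3, so 34, against 35 stated. That is close enough. The allowance covers only loss before the intervention. The plan states no figure for PG-SGA.

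**Later loss.** Using mortality of 10-30% as a proxy, 30 x 0.10 = 3 to 30 x 0.30 = 9 patients would lack a Y1 score.

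**Simulation set-up (all assumed).** Six visits, flat true mean, unit SD at each visit. Within-patient correlation was 0.3, 0.5 or 0.7, under compound symmetry or AR(1). Loss by Y1 was 10, 20 or 30%, either at random or with log-odds rising 1.5 per SD of the NPE score, the previous visit's score, or the current unseen score. The estimate is Y1 minus NPE, so negative means nutrition looks better than it is. The mixed-model column is maximum likelihood with unstructured covariance.

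| Loss driven by | Loss | Unpaired (SD) | Paired completers (SD) | Mixed model (SD) |
|---|---|---|---|---|
| Earlier observed score | 10% | 0.00 to -0.09 | +0.01 to +0.13 | within 0.005 of 0 |
| Earlier observed score | 20% | 0.00 to -0.18 | +0.01 to +0.25 | within 0.005 of 0 |
| Earlier observed score | 30% | 0.00 to -0.27 | +0.02 to +0.36 | within 0.005 of 0 |
| Current unseen score | 10% | -0.04 to -0.10 | -0.01 to -0.03 | -0.03 to -0.04 |
| Current unseen score | 20% | -0.08 to -0.20 | -0.02 to -0.06 | -0.06 to -0.09 |
| Current unseen score | 30% | -0.13 to -0.30 | -0.03 to -0.09 | -0.09 to -0.14 |

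With random loss, all three methods were within 0.005 SD of zero.

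**Why the paired test can point to worse.** Suppose loss follows the NPE score, and let m be the shift in completers' mean NPE score and r the NPE-Y1 correlation. The unpaired bias is r x m and the paired bias is r x m - m = -(1 - r) x m. With compound symmetry at 0.5 and 30% loss, the simulated values were -0.178 and +0.184, so m = -0.178 - 0.184 = -0.362. The formulas then give -0.181 and +0.181, which agrees. The +0.36 end comes from AR(1) at 0.3, where r = 0.3^5 = 0.002 and the paired bias is nearly -m. Under compound symmetry the largest paired value was +0.25.

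**Varying slopes.** With patient slopes added and loss following the last observed score (logit = -2.6 + b x score from the third visit, b = 0.8 or 1.2), the paired bias changes sign. For slope SD of 0.1-0.3 baseline SD per visit and 17-25% lost, it is -0.02 to -0.29 SD, against -0.09 to -0.41 for all available values. With slope SD zero, the paired bias is 0.00.

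**Error rates at n = 30** (compound symmetry 0.5, 30% loss, nominal 2.5% per side). The unpaired test falsely shows improvement in 3.8% (NPE-driven), 5.0% (previous visit) and 8.2% (current score) of trials. Under random loss the figure is 0.5%, because the test ignores within-patient correlation. The paired test falsely shows improvement in 0.4-4.1%, and false worsening reaches 13.5% when loss follows the NPE score.

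**The case against.** The strongest reply is that little depends on this. The primary hypothesis (section 6.2) concerns completion of training sessions, PG-SGA is secondary, and descriptive summaries are planned for every variable. The mixed-model list is also open-ended, and the t-test sentence goes on to correlate its results with outcomes, so the authors may have seen PG-SGA partly as an explanatory variable. The low stakes stand. The open list does not help, because PG-SGA is named in the other sentence, and no other analysis of its course is given.

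A reader might infer that the t-test will make nutrition look better than it is, because sicker patients leave. The documents do not support that. They do not say whether the test is paired. A paired test, the natural reading for one arm, is pushed toward worse when loss follows earlier scores and toward better only when slopes vary enough or loss follows the unseen score. Biases as large as -0.61 SD (available values) or -0.43 SD (paired) can be produced, but only with slope SD 0.3 per visit and about 37% loss. That makes the Y1 SD sqrt(1 + (5 x 0.3)^2) = 1.8 times baseline. The documents give no such slopes, and 37% exceeds their mortality range.

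It is also fair to object that the mixed model is no complete cure. Under loss driven by the unseen score it stays biased, and the paired test did somewhat better there. It also does not define what is estimated after death. Both points stand and shape the fix.

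**Conclusion.** The inconsistency is certain from the text: a six-visit score on the same schedule as FACT-BMT and EQ-5D-5L is sent to an unspecified two-mean test. The consequence is a possible bias whose sign depends on which t-test is used and why patients are lost. For 10-30% loss following earlier observed scores, it is 0 to about -0.27 SD unpaired, about 0 to +0.36 SD paired, and about 0 for the mixed model. If loss follows unseen scores, the mixed model is off by about -0.03 to -0.14 SD.

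These sizes rest on assumed correlations, a fairly strong assumed selection effect, and mortality as a stand-in for total loss. The documents give no SD for PG-SGA, so I cannot convert them to points. The near-zero mixed-model figures come from an unstructured covariance. A simpler structure shares that protection only as far as it fits. I rate this a cheap improvement.

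**What to change.** In section 6.0:

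- Move PG-SGA and the other continuous scores collected at 6T into the mixed-model sentence. Use visit as a categorical factor, all visits including NPE as outcomes, and a patient random intercept, plus a random slope if the model converges.
- Name a simpler covariance structure as fallback. An unstructured matrix for six visits has 6 x 7/2 = 21 parameters, which is a lot for about 30 patients.
- Keep t-tests for quantities with one value per patient.
- State either that estimates after death are conditional on the model or that they are restricted to patients alive at the visit.
- Add a sensitivity analysis for missing visits that lets unseen scores be worse than predicted.

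The cost is a few sentences and slightly more analysis work. The model and software are already in the plan, and no data collection changes.

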2.9 Summary

There is the potential to improve these areas during the 2-3 month window between new patient evaluation and HCT. Much of the literature has focused on improving health indicators during the transplant process to support better outcomes post-HCT. However, the question we want to answer is: can patients improve their health and function pre-HCT and, thus, improve outcomes post-HCT? We are aware of only one intervention taking a similar, but not identical approach.⁸¹ Uniquely, we will target patient participants at their initial evaluation, prior to hospital admission, and follow them throughout the transplant process to discharge, providing them with consistent, evidenced-based physical activity, diet, cognitive, social, and emotional interventions. Our hope is to improve patient outcomes and quality of life by intervening prior to HCT.

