4.0 STUDY PROCEDURES AND ENDPOINTS

Those who consent to participate in R-POP will return within one month (preferably within two weeks) for a separate day of assessments (e.g. cardiopulmonary exercise testing), nutrition education (e.g. what constitutes a serving of protein), and training on how to use iOS devices (e.g. iPad, iPhone) and activity trackers (e.g. Apple Watch), which will be provided to patients for their use during the duration of study participation. In their 2011 report the World Health Organization states that, “the use of mobile and wireless technologies to support the achievement of health objectives (mHealth) has the potential to transform the face of health service delivery across the globe,”⁸² and this investigation will contribute to solidifying use of a mHealth platform with all Duke HCT patients. iPad or iPhones will be pre-loaded with apps and/or PDFs which may include (1) SplendoFit (2) Technology Recordings to better Understand BMT (TRU-BMT), developed by co-Is [name] and [name] to monitor patient reported outcomes of health, quality of life, and nutrition (Duke IRB Pro00068979), (3) an electronic copy of the Duke ABMT Patient Handbook (this is an electronic version of a paper handbook that is given to all transplant patients as part of standard of care), and (4) an electronic copy of Duke ABMT Recipes for Transplant Patients (this is an electronic copy of paper recipes available to all transplant patients as part of standard of care). (5) Jabber, or a similar program, to facilitate video communication (e.g. for monitoring and support of exercise sessions); (6) recipes for meals and smoothies for HCT prepared by collaborator [name] (registered dietitian).

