For the interval training intervention, patients will be asked to complete up to 3 x 30-minute structured high intensity interval training aerobic exercise sessions/week. The structured aerobic exercise will incorporate an intensity specific interval training design with intensities relative to each patient's individual fitness and thus comparable between patients. Heart rates and intensities will be determined from the maximal exercise test (CPET). The preferred mode will be walking, however if the patient prefers swimming or cycling we will adapt the plan accordingly. For the first session, patients will come to the Duke Center for Living for in person evaluation and training. Patients will be asked to wear a chest heart rate strap which will connect with the heart rate monitor. This will ensure accurate heart rate at higher intensity activities. Patients will also wear an Apple Watch and results of heart rate monitoring on the watch will be compared to the chest strap. Before and after each session patients will engage in an active 5-minute warm-up and cool-down at an intensity corresponding to 40%-50% VO_{2peak} . In our experience this is similar to a slow, leisurely walk. Following the warm-up, patients will increase speed to correspond with an intensity of approximately 80% VO_{2peak} for 1-minute before returning to warm-up speed for 1-minute (50% VO_{2peak}). In our experience this is similar to a brisk uphill walk, or climbing stairs. Patients will complete up to 10 of each vigorous intensity (80%) 1-minute interval and 10 of each low intensity (50%) 1-minute interval, or 30-minutes total exercise (including warm-up and cool-down). This type of training has been shown to be safe and feasible in breast and prostate cancer while improving fitness rapidly with little fatigue and few adverse events.⁸⁹ After the initial training session in person, a subsequent training session will take place at the patient's home via iPad/iPhone videoconference using a device provided to the patient to provide additional support and the opportunity to answer questions. Subsequent sessions will be done independently by patients, but study staff will be available via iPad/iPhone if questions arise.

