Skin Swab – risk of mild discomfort and irritation from skin swabbing, self-limited and will stop on request, minimal risk

Stool Collection – risk of mess with transferring stool sample from hat into collection container, minimal risk

Blood collection – care will be taken to prevent excess blood draw, minimal risk

Interval Training – While there are risks associated with any exercise activity, such as chest pain, shortness of breath, muscle cramping or discomfort, musculoskeletal injury, exacerbation of underlying coronary disease,

**A Research Program Targeting Pre-, Peri-, and Post-transplant Optimization Program
(R-POP)**

Version 1.18: October 25, 2022

Page 26

patient with a known history of at-risk coronary conditions will be excluded, as with patients with abnormal findings on CPET testing. To ensure the utmost safety of our participants going through exercise training, study staff will ensure that all patients who take beta-blockers will have taken their medication prior to training to avoid any blood pressure-related events. Furthermore, the first training session will be performed in a monitored setting by trained professionals; the second session (first session at home) will be performed over a monitored video link by trained professionals, which will also occur weekly the first month, monthly for the remainder of the study, and as needed or requested by study staff or subjects; subjects always have the option to return in person for additional sessions. Therefore, these risks will be mitigated by supervision and training and this intervention is deemed low risk.

Referral to psychology/psychiatry, if warranted – while there may be risks of patient psychological distress associated with this referral, the likelihood of benefit from seeing a psychologist/psychiatrist to someone with potential depression or PTSD is outweighed by the risks. There may be financial risks associated with psychology/psychiatry referrals depending on insurance. Low risk.

Additional referral to social work, if warranted – while there may be risks of patient psychological distress associated with this referral, the likelihood of benefit from seeing a social worker to someone with social support needs is outweighed by the risks. Low risk.

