Protections against risks associated with exercise are described above. To review: while there are risks associated with any exercise activity, such as chest pain, shortness of breath, muscle cramping or discomfort, musculoskeletal injury, exacerbation of underlying coronary disease, patients with a known history of at-risk coronary conditions will be excluded. Furthermore, cardiopulmonary exercise testing will be performed as an

A Research Program Targeting Pre-, Peri-, and Post-transplant Optimization Program (R-POP)

Version 1.18: October 25, 2022

additional precaution prior to allowing patients to participate in the exercise intervention. While CPET testing is an exercise itself and has risks, this activity will be performed in a monitored setting by trained professionals. To ensure the utmost safety of our participants going through exercise training, study staff will ensure that all patients who take beta-blockers will have taken their medication prior to training to avoid any blood pressure-related events. Similarly, subjects undergoing interval training will also continue to take their beta-blockers and other medications.

With regard to interval training, the first training session will be performed in a monitored setting by trained professionals; the second session (first session at home) will be performed over a monitored video link by trained professionals, which will also occur weekly the first month, monthly for the remainder of the study, and as needed or requested by study staff or subjects; subjects always have the option to return in person for additional sessions. Therefore, these risks will be mitigated by supervision and training and this intervention is deemed low risk.

Plans for ensuring necessary medical or professional intervention in the event of adverse effects on participants

Initial assessments will take place in person with trained medical staff available to respond either immediately (e.g. CPET testing, interval training) or within 24 hours (e.g. psychological distress brought up by questionnaires/surveys). While adverse events may arise after patients return home, study staff will be available 24 hours a day, seven days a week, to respond to patient concerns and direct them to appropriate care. In fact, the TRU-BMT app and SplendoFit app both contain a tab for contact information and who to call at what time.

Plans for handling incidental findings

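### Section 6.0 sets a raw count of exercise days against unnamed outcomes with no counting window, denominator or time origin; counted over the whole study and related to survival, exercise could look protective with no effect

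*Combined protocol and SAP*

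**What the plan says.** Section 6.0 assigns a method to each type of variable. Longitudinal scores such as FACT-BMT and EQ-5D-5L get linear mixed models. TRM gets Kaplan-Meier, log-rank and Cox methods. Other continuous results, with PG-SGA and the exercise measures as examples ("numbers of days exercised and amount of exercise per day) will be analyzed using standard t-test approaches and correlated with outcomes"), get t-tests and correlation. All secondary and additional analyses are tested at 0.05. No window, denominator, named outcome, landmark or time-dependent covariate is given for the exercise analysis.

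Other sections bear on the counting period but do not settle it:

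- **Pre-transplant.** Section 2.9 asks whether improving health before transplant improves results after it. Section 7.0 places the benefit in a pre-transplant period of median 101 days, and says the study would inform a randomised trial of pre-transplant interventions.
- **To discharge.** Section 2.9 also says the team will "follow them throughout the transplant process to discharge" while delivering the interventions. Section 4.0 defines that visit as "discharge home [DC] (approximately D90").
- **Whole study.** Trackers are "provided to patients for their use during the duration of study participation" and activity capture is listed as continuous ("Data will be collected passively from the Apple Watch"; section 4.0). Video supervision runs "weekly the first month, monthly for the remainder of the study" (section 7.0, stated twice).

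The interval training text in section 4.1.1 sets up to three sessions a week. After the first two, "Subsequent sessions will be done independently by patients", with no end date.

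**The concern.** A raw count of exercise days depends on how long the patient was there to exercise. If the count runs through follow-up and the outcome is death, a patient who dies at day 60 after transplant loses about 300 days in which to exercise. The count is then low because of the death, and exercise appears protective even if it does nothing. This is immortal-time bias.

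The route to it is open. Overall and disease-free survival are listed endpoints (section 1.2.2), and how physical activity affects outcomes is the first item of secondary objective 1.2.1. Because the window is not fixed, it can also be chosen after the data are seen. The harm would be a misleading exploratory signal carried into the design of the phase 2 trial.

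**Working it through.** The plan gives no figure for this analysis, so there is none to reproduce. The check asks how often a 5% test is significant when exercise has no effect.

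**Inputs from the documents.** 30 trained patients (section 3.5); 101 pre-transplant days (section 7.0); up to 3 sessions a week, that is 3/7 a day (section 4.1.1); alpha 0.05 (section 6.0).

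**Assumptions.** One-year mortality 10-30%. Section 7.0 gives this range for TRM without a time horizon, and section 2.0 gives 20-30%. Deaths are exponential after transplant. Adherence is Beta(2,2) (mean 0.5, variance 0.05), independent of survival. After transplant the exercise rate is multiplied by f. The test is two-sided.

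**Expected gap in days, survivors minus deaths.** With one-year mortality m and L = -ln(1 - m), the mean death time among first-year deaths is 365/L - 365(1 - m)/m.

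- m = 10%: 3464.3 - 3285.0 = 179.3 days, so 185.7 days are lost.
- m = 20%: 1635.7 - 1460.0 = 175.7, so 189.3 are lost.
- m = 30%: 1023.3 - 851.7 = 171.7, so 193.3 are lost.

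Gap = days lost x 3/7 x 0.5 x f. At f = 1 this is 39.8, 40.6 and 41.4 exercise days. At 30% mortality it is 10.4 for f = 1/4 and 4.1 for f = 1/10. For a count stopped at D90 with f = 1, about 12.8 days are lost on average, a gap of 2.7.

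**Gap against spread at 30% mortality.** The SD of survivors' counts from adherence alone is (101 + follow-up days x f) x 3/7 x √0.05.

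- Year 1, f = 1: 466 x 3/7 x 0.2236 = 44.7; ratio 41.4/44.7 = 0.93.
- Year 1, f = 1/4: 192.25 x 3/7 x 0.2236 = 18.4; ratio 0.56.
- Year 1, f = 1/10: 137.5 x 3/7 x 0.2236 = 13.2; ratio 0.31.
- D90, f = 1: 191 x 3/7 x 0.2236 = 18.3; ratio 0.15.

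**Simulated false-positive rate** (t-test of days, dead versus alive at Year 1; trials with at least 2 deaths):

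| Count | 10% mortality | 20% | 30% |
|---|---|---|---|
| Year 1, rate unchanged | 30% | 49% | 63% |
| Year 1, rate a quarter | 10-11% | 17-18% | 25-26% |
| Year 1, rate a tenth | 5% | 8% | 10% |
| To D90, rate unchanged | 5% | 6% | 6% |
| To transplant, all reach it | 4-6% | 4-6% | 4-6% |

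About 18% of trials at 10% mortality have fewer than 2 deaths. Counted over all trials, the unchanged-rate figure at 10% mortality is about 25%.

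**Sensitivity.**

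- Across polarised Beta(0.7,0.7) to more uniform Beta(4,4) adherence, the Year 1 figures run 12-83% (unchanged) and 5-42% (quarter).
- If about 40% of first-year deaths fall by D90, the D90 count gives 4-13%.
- If an assumed 5-10% die before transplant and stay in, a raw pre-transplant count gives 5-19%.
- If the outcome is measured only in Year 1 survivors, everyone has the same post-transplant window; the rate was 5.1% (Year 1 count, unchanged rate, 30% mortality).

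**Repair.** A weekly pre-transplant rate, with survival counted from Day 0 in transplanted patients, gives 4-5%. Dividing a whole-study count by time alive does not repair it unless the rate is constant: it gives 11-21% at half rate and 22-56% at a quarter, mostly with those who died appearing to exercise more.

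**The case against.** The strongest reply is that the biased analysis has to be assembled. Section 6.0 never ties the exercise correlation to survival, and the same paragraph gives TRM its own time-to-event methods. Objective 1.2.1 covers wellness and quality of life as well, so FACT-BMT or EQ-5D-5L are equally natural targets, and in Year 1 survivors they are not exposed. The t-test and the correlation become the same test only once the outcome is coded dead or alive. The whole-study window is also the least directly supported: holding a tracker does not define an analysis count, and the study question concerns the period before transplant. Finally, an unchanged exercise rate through conditioning and recovery is implausible when section 4.0 makes even the Day 30 exercise test depend on medical stability.

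Most of this stands, and it limits the size of the point. A reader might infer that the plan prescribes a biased survival analysis, or that 30-63% is its error rate. The documents support neither. It is also right that amount of exercise per day, listed alongside the count, is not mechanically shortened by death. What remains is that the text neither requires nor excludes the harmful combination, and no other section closes the gap.

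**Conclusion.** The point holds as a minor one: the exercise analysis is under-specified, and one reading the text permits can produce a false survival benefit. Under that reading the false-positive rate is about 5-10% if post-transplant exercise falls to a tenth, 10-25% at a quarter, and 30-63% only if it is unchanged. These figures are illustrative. They rest on assumed mortality, exponential deaths and Beta(2,2) adherence, none of which the documents fix. The direction does not depend on those choices. A count to transplant with all patients reaching it, or to D90 with exponential deaths, is near nominal.

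A reader might also infer that the primary hypothesis is out of reach of this gap. The correlation does not alter it. However, section 6.2 asks whether at least half of enrolled patients complete over half of their sessions, and without an end to the training period the number of sessions due is undefined there too.

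**What to change.** In section 6.0, for analyses of exercise against survival-type outcomes:

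1. Replace the raw count with completed sessions per available week, from first training session to sign-off, and define a completed session and an available week.
2. Relate it to overall survival and TRM counted from Day 0 among transplanted patients (a landmark analysis).
3. Describe peri- and post-transplant exercise by phase, or enter it only as a time-dependent covariate.
4. Report estimates with 95% confidence intervals, labelled exploratory.
5. State two limits: patients never transplanted leave this analysis, and reverse causation (sicker patients exercise less) remains.

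The study team should also reconcile sections 2.9, 4.1.1 and 7.0 on when training ends, so that the session denominator in section 6.2 is defined.

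The cost is wording; no new data are needed. The analysis set shrinks somewhat. If an assumed 10-20% are never transplanted, 30 becomes 27 to 24, and the smallest |r| significant at 0.05 rises from 0.36 to 0.38-0.40.

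A separate improvement costs nothing: PG-SGA is collected at all six main timepoints (section 4.0), so analyse it with the linear mixed model already planned for FACT-BMT and EQ-5D-5L instead of t-tests.
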